12.2.1 Safety Review

A review of adverse events will be done by the PI weekly. This will be done through review of the survey data. More frequent review may need to occur if SAE's will be identified and reported to the IRB within 5 days as stated in section 9.4.2

12.2.2 Efficacy Review

This study is an optimization study and seeks to optimize a low cost FNS for clinical use.

12.3 Final Analysis Plan

Statistical Analysis – Aim 1: Optimization Phase.

1. Outcome 1 (Primary): The primary outcome is ease of use comparison between the FNS to the SOC scope (score of 1 – 5, with 1 being very hard and 5 being very easy).
2. Outcome 2 (Secondary): Quality of the image (image quality score range 1-5, with 1 being poor and 5 being excellent).
3. Outcome 3 (Secondary): Perceived pain between the FNS to the SOC scope (pain score range of 1 – 3, with 1 being much more and 3 being much less).

Scenario 1:

Success of this first phase 1 (Aim 1) after evaluating 37 subjects is defined as - (1) at least 90% response of ease of use of second scope compared to first score to range from same to excellent (3 to 5); and (2) 90% responding to better video quality of second scope compared to first (score ranging from same to excellent (3 to 5); and (3) 90% responding to pain score of same or much less (2 or 3); In short, this phase is a success if 90% respond to same to excellent/much less on all 3 of the outcomes.

[figure not shown]
Scenario 2: If the rate is between 50 to < 90% for any three outcomes in a sample from 37, then the plan is to proceed recruiting more subjects until 50 are recruited. At 50 subjects, if in scenario 1 then phase 1 is a success and phase 1 is complete; if not, fine tune the prototype.

Scenario 3: If the rate is < 50% for any one of the 3 outcomes described above, then the plan is to proceed to fine tuning the prototype.

The primary outcome of ease of use of scope as reported by the physicians, will be examined between the two different scopes, at the simplest level, using paired Z-test if the scores (or transformed scores) are normally distributed or by using Wilcoxon test if the scores are non-normal.

The analysis for secondary outcomes of the change in the quality of the videos and pain will each be examined using paired Z-test, if the change (or transformed scores) is normally distributed or by Wilcoxon test if the change is non-normal. Assumptions of each of these tests will be examined. The significance of each of the outcomes will be examined at alpha = 0.05. The reliability of this instrument (using intra-class-correlation (ICC)) will be first assessed by using the data from the first 50 subjects. If ICC is < 0.9, we will include training component and necessary adjustment for the physicians.

See diagram below

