3 OBJECTIVES AND OUTCOME MEASURES

OBJECTIVES:

We will collect user feedback and reliability of the low-cost FNS scope as compared with the currently used SOC scope procedure. Collection of technical issues with the low cost FNS prototypes will also include steering, lighting, video, fogging, image capture.

Key objectives include comparisons between the SOC scope and FNS:

Primary

Ease of use

Compared with the first scope, how easy was the second scope to use?

Very Hard	Harder	same	Easier	Very Easy
1	2	3	4	5

Secondary

1) Image Quality

Rate the video quality of the first scope: (Poor) 1 2 3 4 5 (Excellent)

Rate the video quality of the second scope: (Poor) 1 2 3 4 5 (Excellent)

2) Perceived pain by subjects

Did you experience more, the same, or less pain/discomfort with the second scope compared with the first scope?

much more about the same much less

1	2	3
---	---	---

OUTCOME MEASURES

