3.1 Primary

Objective	Brief Description/Justification of Outcome Measure	Outcome Measured By	Time Frame
Assess ease of use by end users between the SOC scope and FNS	We are comparing the ease of use between the FNS to the SOC scope. This will impact the design considerations and modification for the prototype optimization.	Compared with the first scope, how easy was the second scope to use? Very Hard 1 Harder 2 Same 3 Easier 4 Very Easy 5	Up to 2 months

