3.2 Secondary

Objective	Brief Description/Justification of Outcome Measure	Outcome Measured By	Time Frame
Assess image quality and subject pain	Comparison of image quality between the SOC scope and FNS as well as subject perception of pain between the two exams will help to inform modifications needed for prototype optimization.	image quality of each scope: rated 1(poor) to 5 (excellent) perceived pain by subjects between scopes: Much More 1 About the same 2 Much Less 3	up to 2 months

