This technical and subjective feedback from subjects and providers will be used to optimize the device during the Optimization Phase. Each outcome measure as described in Section 3.1 and 3.2 will be compared between the SOC scope to the low cost FNS and used as a basis for modifications. For example, if the low-cost FNS image quality is noted to have lower ratings compared to the SOC scope due to inadequate lighting, modifications will be made to increase the light output for the next prototype.

The goal is to modify the prototype so that the outcome measures from the low cost FNS meet or exceed the outcome measures from the SOC scope. If this is the case, no

further prototypes will need to be performed for the optimization phase. Thus, the threshold for success will be noninferiority of the FNS compared to the SOC scope.

In addition to survey feedback, the FNS will have capacity to capture anonymized images of the upper aerodigestive tract such as the oropharynx, larynx, and nasopharynx. These will be collected and stored to a centralized image library. There will be no link to the subject, thus preventing loss of confidentiality.

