If harder or very hard: please explain:

Quality of Images: Aim 1

Rate the video quality of the first scope: (Poor) 1 2 3 4 5 (Excellent)

Rate the video quality of the second scope: (Poor) 1 2 3 4 5 (Excellent)

Did the subject experience an AE: Y / N

If yes - please provide additional information below:

Name of adverse event: _____

Brief description of the problem or event:

Severity of adverse event (using scale below):

1. Mild: no intervention required
2. Moderate: minimal, local, or non-invasive intervention indicated
3. Severe: significant symptoms requiring invasive intervention; subject seeks medical attention

Is the adverse event related to study procedure?

1. **If related**, please specify: Possibly, Probably, or Definitely related
 - a) The event is known to occur with the study intervention, and/or
 - b) There is a temporal relationship between the intervention and event onset and/or
 - c) The event abates when the intervention is discontinued, and/or
 - d) The event reappears upon a re-challenge with the intervention.
2. **If not related**, please specify if unlikely related or Not Related)
 - a) There is no temporal relationship between the intervention and event onset, and/or
 - b) An alternate etiology has been established.

Is the problem/event unexpected? Y/N

Does the event meet the definition of a serious adverse event? Y/N

If yes, check criteria below:

A serious adverse event (SAE) is one that meets one or more of the following criteria:

1. Results in death

-
- 2. Is life-threatening (places the subject at immediate risk of death from the event as it occurred)
 - 3. Results in inpatient hospitalization or prolongation of existing hospitalization
 - 4. Results in a persistent or significant disability or incapacity

An important medical event that may not result in death, be life threatening, or require hospitalization may be considered an SAE when, based upon appropriate medical judgment, the event may jeopardize the subject and may require medical or surgical intervention to prevent one of the outcomes listed in this definition.

Outcome of adverse event: resolved or unresolved

Date of resolution:

For enrolled subjects

Pain Comparison: Aim 1-secondary objective

Did you experience more, the same, or less pain/discomfort with the second scope compared with the first scope?

much more about the same much less

1 2 3

CONSENT FORM FOR PARTICIPATING IN RESEARCH

Duke's IRB approved consent form will be provided separately

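### The image-quality part of Scenario 1 is worded as a comparison with the SOC scope, but its 3-to-5 band fits only the absolute FNS rating

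*Combined protocol and SAP*

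**What the plan says.** Scenario 1 in section 12.3 defines phase success after 37 subjects by three components, each requiring 90%. The image-quality component is "90% responding to better video quality of second scope compared to first (score ranging from same to excellent (3 to 5". The same section then summarises the rule as a same-or-better response on all three outcomes. Scenario 2 continues to 50 subjects when rates lie between 50% and just under 90%. Scenario 3 sends the prototype to fine tuning if any one outcome is below 50%.

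The data collected are two separate ratings. The post-procedural survey in the Supplemental Materials asks "Rate the video quality of the first scope: (Poor) 1 2 3 4 5 (Excellent", and the companion item, also printed in section 3, is "Rate the video quality of the second scope: (Poor) 1 2 3 4 5 (Excellent". Section 3.2 describes the outcome in the same way: "image quality of each scope: rated 1(poor) to 5 (excellent". The only five-point item on which 3 means *same* is ease of use in section 3.1: "Very Hard 1 Harder 2 Same 3 Easier 4 Very Easy 5".

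Section 4 sets the goal that the FNS results "meet or exceed the outcome measures from the SOC scope". Its example of a reason to modify the device is "if the low-cost FNS image quality is noted to have lower ratings compared to the SOC scope". Section 12.1 states the non-inferiority hypothesis for image quality as well as for ease of use and pain. Section 12.3 also says that "the change in the quality of the videos and pain will each be examined using paired Z-test" (or a Wilcoxon test), but no scenario refers to that test.

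**The concern.** The criterion cannot be matched to any collected variable. *Better* and the reference to the first scope call for a comparison. *Same* allows ties, which contradicts *better*. The band 3 to 5 and the word *excellent* belong to the absolute scale of a single scope, and that scale has no *same* response. The label therefore mixes the anchors of two different items.

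Three readings are open: FNS rated 3 or more, FNS at least equal to SOC, and FNS strictly better than SOC. All three components must reach 90%, and one below 50% is enough for Scenario 3, so the reading can decide the phase. With no rule fixed, the choice could be made after the ratings are seen. The reading that fits the printed band is also the one that leaves SOC out, so it cannot support a non-inferiority claim on image quality.

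**Working it through.** **Inputs.** From section 12.3: 37 subjects, extended to 50 if needed; success at 90%; fine tuning below 50%. From section 3 and the survey: two ratings per subject, each 1 to 5. The documents give no expected rating distributions, so any used below are labelled as assumptions.

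**The plan's own figure.** Section 12.2 gives n = 37 for a two-sided 95% interval of width 0.2 at a proportion of 0.9, with limits 0.76 and 0.96. The Wilson score interval has centre (p + z²/2n)/(1 + z²/n) and half-width z√(p(1−p)/n + z²/4n²)/(1 + z²/n). With p = 0.9, n = 37 and z = 1.96 it gives 0.763 to 0.962, width 0.199, and 37 is the smallest n with width at most 0.2. The figure reproduces. It does not depend on this point, which concerns what counts as a success.

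**Counts needed.** 0.9 × 37 = 33.3, so 34/37 (91.9%). 0.9 × 50 = 45. 0.5 × 37 = 18.5, so 18 or fewer is Scenario 3 and 19 to 33 is the Scenario 2 range.

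**Where the readings differ.** There are 25 possible (FNS, SOC) pairs. FNS ≥ 3 counts 15 as success, FNS ≥ SOC counts 15, and FNS > SOC counts 10. The first two sets are not the same:
- (3,4), (3,5) and (4,5) pass FNS ≥ 3 although the FNS is rated worse.
- (1,1), (2,1) and (2,2) fail it although the FNS is equal or better.

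**Limiting cases, successes out of 37** (these follow from the scales alone):

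| Ratings in every subject | FNS 3 to 5 | FNS ≥ SOC | FNS > SOC |
|---|---|---|---|
| SOC 5, FNS 3 | 37 | 0 | 0 |
| Both 4 | 37 | 37 | 0 |
| Both 2 | 0 | 37 | 0 |

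**A less extreme illustration (assumed marginals).** Let SOC be 4 or 5 in 30% and 70%, and FNS 3, 4 or 5 in 40%, 40% and 20%.
- FNS 3 to 5: 100%.
- FNS ≥ SOC with independent ratings: 0.3 × (0.4 + 0.2) + 0.7 × 0.2 = 0.32.
- FNS ≥ SOC over every joint distribution with these marginals: 0.20 to 0.50. The minimum is reached when only the FNS 5s succeed. The maximum is 0.2 (FNS 5 paired with SOC 5) plus 0.3 (FNS 4 paired with SOC 4).
- Mean difference: 3.8 − 4.7 = −0.9 points.

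So the component passes fully on one reading while at most half the subjects rate the FNS as equal or better.

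**Behaviour of the paired rule for a truly equal scope (assumed discordance).** If the two ratings differ in a fraction d of subjects, equally often in each direction, then P(FNS ≥ SOC) = 1 − d/2. Binomial tails give:

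| d | P(FNS ≥ SOC) | ≥ 34/37 | ≥ 45/50 | Both looks |
|---|---|---|---|---|
| 10% | 0.95 | 0.888 | 0.962 | 0.967 |
| 20% | 0.90 | 0.486 | 0.616 | 0.651 |
| 30% | 0.85 | 0.174 | 0.219 | 0.258 |

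The last column is P(X₃₇ ≥ 34) + Σ P(X₃₇ = x) × P(Bin(13, p) ≥ 45 − x), summed over x = 19 to 33, with p = 1 − d/2. It is for this component alone.

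**The case against.** The strongest reply is that the intent can largely be recovered. The reference to the first scope, the summary sentence in section 12.3, the match-or-surpass goal in section 4, the non-inferiority hypothesis in section 12.1 and the planned paired analysis all point to FNS at least equal to SOC. Scenario 1 also uses *excellent* for ease of use, whose scale has no such anchor, so the phrase may be loose shorthand and not a deliberate absolute cut-off. Section 4 says each outcome will be compared between scopes and used as a basis for modification, so an image deficit need not go unnoticed. Ease of use and pain are truly comparative and must also pass. The decision diagram in section 12.3 is not shown in the text available and might supply a derivation. Image quality is a secondary outcome in a single-site optimisation study, and the limiting cases show that the decision can flip, not that it is likely to.

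Much of this is fair, and the evidence of intent is why the fix adopts the paired reading. But the printed criterion still says *better* and *3 to 5*, and neither means equal or better on paired ratings. The modification language in section 4 and the paired test do not define or override the scenario rule. Ease of use and pain do not measure image quality. A diagram that gave a paired derivation would contradict the written criterion, which would still need correcting. The outcome is secondary by label, but in Scenario 1 it is mandatory for success.

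**Conclusion.** The point holds and must be fixed before the ratings are reviewed. As written, a mandatory component of the success rule does not correspond to any collected response. The one variable that fits its numerical band allows a pass at 37/37 when every FNS image is rated below SOC, where a paired comparison gives 0/37. That these readings can reverse the decision follows from the scales alone. The 32% (20% to 50%) illustration and the noise figures rest on assumed distributions. Confidence in the mismatch in the text is high; the statement that the component cannot be computed unambiguously is subject to what the diagram shows.

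**What to change.** In section 12.3, derive the component from the paired ratings: a subject is a success if FNS rating minus SOC rating is at least 0, and at least 90% must succeed (34/37, or 45/50 at the second look). Remove *better* and the 3-to-5 band for this outcome, apply the same definition in Scenarios 2 and 3, and align the decision diagram. State that the paired test on video quality is supportive and does not drive the scenarios, or say how it does.

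Both ratings are already collected, and n = 37 is unchanged. The cost lies in the operating characteristics. The reported proportion will probably be less favourable than under an absolute cut. A truly equal scope passes this component over both looks with probability of about 97%, 65% or 26% if ratings differ symmetrically in 10%, 20% or 30% of subjects. If the sponsor finds that too strict, a within-subject margin should be prespecified and justified before any data are seen.

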5.4 Participant Withdrawal or Discontinuation from Study Procedures/Intervention

5.4.1 *Reasons for Participant Withdrawal or Discontinuation from Study Procedures/Intervention*

Subjects are free to withdraw from participation in the study at any time upon request.

An investigator may discontinue an individual's participation in an intervention or withdraw an individual from the study if:

- The participant meets an exclusion criterion (either newly developed or not previously recognized) that precludes further study participation.
- Inability to complete the FNS exam (i.e., bilateral nasal obstruction preventing passing of the flexible FNS)

5.4.2 *Handling of Participant Withdrawals from Study or Participant Discontinuation of Study Intervention*

The reason for withdrawal will be solicited from the subject if they choose to stop the investigational scope exam and this will be recorded in the REDCap database.

Replacement participants will be recruited until enrollment is complete. Data that is already collected will be included in the analysis and not destroyed.

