5.5 Premature Termination or Suspension of Study

This study may be suspended or prematurely terminated if there is sufficient reasonable cause. Written notification, documenting the reason for study suspension or termination, will be provided by the suspending or terminating party to the investigator, funding agency (NIDCR), and regulatory authorities. The principal investigator will also promptly inform the IRB and NIDCR and will provide the reason(s) for the termination or suspension.

Circumstances that may warrant termination include, but are not limited to:

- Determination of unexpected, significant, or unacceptable risk to participants.
- Insufficient adherence to protocol requirements.
- Data that are not sufficiently complete and/or evaluable.
- Determination of futility.

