12.2 Sample Size Considerations

Aim 1 is aimed at optimizing the FNS for its optimal functioning as explained in the recruitment described above.

Fixing alpha at 0.05, power at 80%, a sample size of 37 produces a two-sided 95% confidence interval with a width equal to 0.2 when the sample proportion of success is 0.9. The lower and upper confidence interval for this success rate of 0.9. is 0.76 and 0.96 respectively (PASS 16, 2018). Hence at the end of testing on 37 subjects, if the proportion who answer good outcomes as described in scenario 1 is between 0.76 and 0.96, phase one of the study is a success.

Power Analysis and Sample Size Software (2018). NCSS, LLC. Kaysville, Utah, USA, ncss.com/software/pass).

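### Sections 12.2 and 12.3 give conflicting success rules for the same look at 37 subjects

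*Combined protocol and SAP*

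**What the plan says.** Section 12.2 justifies 37 subjects by the width of a two-sided 95% confidence interval, 0.2 at a sample proportion of 0.9, and reports the limits: "The lower and upper confidence interval for this success rate of 0.9. is 0.76 and 0.96 respectively". It then turns those limits into a decision. After 37 subjects, "if the proportion who answer good outcomes as described in scenario 1 is between 0.76 and 0.96", the phase is declared a success.

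Section 12.3 sets the decision out again as three scenarios:

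- **Scenario 1:** success at 37 subjects if at least 90% of responses are favourable on ease of use, on image quality and on pain.
- **Scenario 2:** "If the rate is between 50 to < 90% for any three outcomes in a sample from 37", recruitment goes on to 50. The sentence "At 50 subjects, if in scenario 1 then phase 1 is a success and phase 1 is complete; if not, fine tune the prototype" then applies the same test again to the larger sample.
- **Scenario 3:** "If the rate is < 50% for any one of the 3 outcomes described above", go to fine tuning.

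Section 5.5 lists "Determination of futility" among the grounds for termination, without a numerical rule.

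**The concern.** Both success statements apply to the same 37 subjects, and Section 12.2 refers to Scenario 1 for what counts as a good outcome, so they cannot be taken as rules for different questions. One accepts proportions well below 90% and has an upper limit. The other starts at 90% and has none. For many plausible results, the reader cannot tell whether the phase has succeeded.

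This decision carries the study. Under Sections 4 and 12.3, success completes the phase and no further prototype is needed. Otherwise, recruitment continues or the prototype is modified.

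A smaller question follows from Section 12.3 alone: whether Scenario 2 continues to 50 on results that can no longer reach 90%.

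**Working it through.** **Inputs.** From Section 12.2: n = 37, proportion 0.9, interval width 0.2, limits 0.76 and 0.96. From Section 12.3: 90% on all three outcomes, continuation band 50% to <90%, second look at 50. The documents give no true favourable rates, so 0.80 to 0.95 is an assumed range. The counts take the first 37 subjects as part of the 50, with every rating evaluable.

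**1. The plan's own figure.** Wilson interval with z = 1.96, z² = 3.8415:

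- centre = (0.9 + z²/74)/(1 + z²/37) = 0.9519/1.1038 = 0.8624
- half-width = 1.96 × √(0.9×0.1/37 + z²/(4×37²))/1.1038 = 1.96 × 0.05598/1.1038 = 0.0994
- limits 0.763 and 0.962, width 0.199

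At n = 36 the width is 0.202, so 37 is the smallest n with width at most 0.2. The sample size and its limits reproduce. The limits describe uncertainty about the true rate when 0.9 is observed. They are not a range of observed results that would show success.

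**2. The two rules as counts of 37.** Section 12.2: 0.76×37 = 28.1 and 0.96×37 = 35.5, so 29 to 35. Section 12.3: 0.9×37 = 33.3, so 34 to 37.

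| Favourable of 37 | Section 12.2 | Section 12.3 |
|---|---|---|
| 29–31 | success | not a success; cannot reach 90% at 50 |
| 32–33 | success | not yet; continue to 50 |
| 34–35 | success | success |
| 36–37 | outside the stated range | success |

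Section 12.2 does not say whether its proportion is per outcome or joint across the three. The conflict survives either way. If the same 8 subjects rate all three outcomes unfavourably, both the joint proportion and each single proportion are 29/37.

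**3. How often the rules disagree.** Exact binomial with n = 37, one outcome:

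| Assumed true rate | P(29–33) | P(36–37) | Success at 37, Section 12.2 | Success at 37, Section 12.3 |
|---|---|---|---|---|
| 0.80 | 64% | 0.3% | 68% | 4.5% |
| 0.85 | 73% | 1.8% | 89% | 17% |
| 0.90 | 50% | 10% | 89% | 49% |
| 0.95 | 11% | 44% | 56% | 89% |

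**4. Scenario 2's band under the 90% rule.** 0.5×37 = 18.5, so the band is 19 to 33 (15 counts). Success at 50 needs 0.9×50 = 45, and 13 subjects are added. A count of 31 reaches at most 31 + 13 = 44, or 88%. So 19 to 31 (13 counts) cannot succeed. A count of 32 needs 13/13 and 33 needs at least 12/13.

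A floor at 32/37 would save 13 × [P(continue now) − P(continue with floor)] subjects. With a common true rate, independent outcomes and Scenario 3 taking precedence:

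| True rate | Scenario 2 applies if any outcome is in the band | Scenario 2 applies only if all three are |
|---|---|---|
| 0.85 | 13×(0.995−0.130) = 11.2 | 13×(0.564−0.039) = 6.8 |
| 0.90 | 13×(0.885−0.478) = 5.3 | 13×(0.135−0.044) = 1.2 |
| 0.95 | 13×(0.300−0.271) = 0.4 | 13×(0.0014−0.0011) ≈ 0 |

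**The case against.** **Section 12.2 is only a precision statement.** The interval is a correct precision statement and N = 37 stands. But the text goes on to attach the word success to an observed proportion inside the interval, and that sentence cannot be read as precision alone.

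**The diagram may settle it.** The decision diagram in Section 12.3 is not available here and could clarify how Scenario 2 handles mixed results. It would not remove the explicit sentence in Section 12.2.

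**36 or 37 of 37 as failure.** A reader might infer that Section 12.2 fails the best possible results. It does not say so. It leaves them outside its success range without naming a consequence, which is a drafting gap and not a reversed verdict.

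**Scenario 2 as the main fault.** A reader might infer from 13 of 15 counts that most continuing cohorts are wasted, or that the missing floor could let a poor prototype through. Neither follows. The counts are not equally likely, and the saving ranges from about 11 subjects to almost none. A result that cannot reach 45/50 ends in fine tuning either way, so the probability of success does not change. Sections 4 and 5.3 also plan up to 50 subjects per prototype and use their ratings to improve it, so subjects 38 to 50 serve a stated purpose. What stands is that Scenario 2 does not give that as its reason.

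**Conclusion.** The plan is wrong as written on its main decision: Sections 12.2 and 12.3 cannot both be the success rule at 37 subjects. They agree on success only at 34 and 35 of 37. The material conflict is at 29 to 33, where Section 12.2 ends the phase as a success and Section 12.3 does not. At assumed true rates from 0.80 to 0.90, a single outcome falls there at least half the time; at 0.95, about one time in nine. The counts follow from the documents. The probabilities rest on the assumed rates, on independent ratings within an outcome, and on a favourable response being defined for each outcome.

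Scenario 2's missing floor is a minor efficiency point. Its size depends on the true rate and on how the condition about three outcomes is read.

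**What to change.** **Main change.** Delete the sentence in Section 12.2 that declares success between 0.76 and 0.96. Keep those limits only as the expected precision when 0.9 is observed. State one rule in both sections: success means at least 90% favourable on each of the three outcomes, i.e. at least 34/37 at the first look or 45/50 at the second, with no upper limit. This keeps Section 12.3's rule, to which Section 12.2 already refers.

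**Minor change.** In Scenario 2, do one of two things. Either continue to 50 only if every outcome has at least 32/37 favourable and otherwise fine tune at 37, or keep the present band and say that subjects 38 to 50 are recruited for design feedback. In the same edit, say whether Scenario 2 needs one or all three outcomes in the band, unless the diagram already does.

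**Cost.** A protocol amendment, which Section 15.2 sends to the IRB and NIDCR. No subjects are added and the sample size justification is unchanged. A floor, if chosen, loses no possible success but gives up to 13 fewer feedback responses per failing prototype.
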